9.2 RESCUE MEDICATION AND RISK MANAGEMENT

Higher doses of Vitamin D may lead to hypervitaminosis D manifested by hypercalcemia and its sequelae. Treatment of acute or chronic intoxication includes withdrawal of Vitamin D3 and any calcium supplements, maintenance of a low calcium diet and if needed corticosteroids or calcuic diuretics, such as furosemide and ethacrynic acid to decrease serum calcium concentrations. All participants will be monitored by site physicians and trained staff should any adverse events arise participants will have access to a phone number and e-mail address provided on the copy of their signed consent form. They will be informed to use these contacts to inform the Principal Investigator about concerns that may be associated with treatment received in each site.

9.3 PREMATURE WITHDRAWAL/DISCONTINUATION CRITERIA

Participants may be withdrawn or be discontinued from the study for any of the following reasons:

1. At the participant's request (withdrawal of consent)
2. At the discretion of the investigator, if deemed appropriate, for any reason
3. If an intolerable or life threatening adverse event occurs

Or if any of the following develop:

4. renal dysfunction
5. dementia
6. severe depression/anxiety/schizophrenia
7. hypercalcaemia and/or hypermagnesemia

Participant data collected to the date of discontinuation or withdrawal will be included in the analysis.

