 72 follows a fractional factorial design as shown in Figure 1. Participants will be recruited
 73 primarily from the community and from clinics serving MCI population across five sites:
 74 London (lead and sponsor site), Waterloo-University of Waterloo, Waterloo-Wilfrid
 75 Laurier University, Montreal, and Vancouver. All eligible participants will be randomized
 76 to 5 arms in 1:1:1:1:1 ratio:

[figure not shown]
77 Arm 1: combined AE and RT exercise + cognitive training + vitamin D

78 Arm 2: combined AE and RT exercise + cognitive training + placebo vitamin D

79 Arm 3: combined AE and RT exercise + control cognitive training + vitamin D

80 Arm 4: combined AE and RT exercise + control cognitive training+ placebo vitamin D

81 Arm 5: BAT exercise + control cognitive training + placebo vitamin D

82 AE: aerobic exercise; RT: progressive resistance training; BAT: balance and toning control

83 Figure 1. Trial design overview

84 5. Study Endpoint

85 The study endpoint will be at 6 Month (post-intervention).

86

87

6. Study Assessment

88 The participant's eligibility will be assessed during the screening visit. Assessment
 89 which will be performed during three visits: baseline, post-intervention at 6 months, and
 90 6-month follow up after the postintervention at 12 months. The measures at each
 91 assessment are described in Table 1.

92

93 Table 1. Assessments across study visits

Procedure	Visit 1 Screening	Visit 2 Baseline	Visit 3 6 month	Telephone Follow-up at 9 month	Visit 4 12 month
Written Informed Consent	X				
Demographic Information	X				
Mini Mental State Examination (MMSE)	X				
Physical Activity Readiness Questionnaire Plus (PARQ +)	X				
Logical Memory 1 & 2	X				
CERAD Word List Recall	X				
PASE Questionnaire	X				
Montreal Cognitive Assessment (MoCA)	X		X		X
Generalized Anxiety Disorder 7 (GAD-7)	X		X		X
Geriatric Depression Scale (GDS-30)	X		X		X
Clinical Dementia Rating (CDR)	X		X		X
Activities of Daily Living (ADCS-ADL and IADL)	X		X		X
Clinical Medical Questionnaire		X	X		X
Dual Task Control Assessment		X	X		X
ADAS-Cog 13 (+ tests ^a)		X	X		X
Trail Making Test A & B ^a		X	X		X
Digit Symbol Test ^a		X	X		X
Digit Span Forward and Backward WAIS-III ^a		X	X		X
Boston Naming Test ^a		X	X		X
Verbal Fluency Test ^a		X	X		X
Colour Word Interference Test		X	X		X
Quality of Life Questionnaire (SF-36)		X	X		X
Short Physical Performance Battery (SPPB)		X	X		X
Gait Assessment using Gait Mats and accelerometers (when available)		X	X		X

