153 AP/PA correction scan = 7 min) to calculate fractional anisotropy and diffusivity in white
154 matter tracts as well as derive tract-based statistics. Cerebrovascular integrity and
155 pathology will be assessed using the following contrasts: PD/T2 = 5 min; FLAIR = 7 min,
156 and T2* = 5 min). Functional magnetic resonance imaging at rest (rsfMRI plus field map
157 = 12 min) will also be acquired to measure change in data-driven functional networks.

158 **9.5 Change in Blood biomarkers measures**

159 Serum biomarkers of inflammation (C reactive protein, and interleukin 6), neuroplasticity
160 (brain-derived neurotropic factor), endothelial health (vascular endothelial growth factor
161 1), and vitamin D serum levels will be measured before and after intervention.

162 **9.6 Covariates**

163 Pre-specified covariates will be age, sex, years of education and number of
164 comorbidities.

165

166 **10. Statistical Analysis**

167 **10.1 Descriptive Analysis**

168 The baseline characteristics will be summarized using means and standard deviation, or
169 medians and interquartile range where appropriate, for continuous characteristics, and
170 frequencies and percentages for categorical variable.

171 **10.2 Primary Efficacy Analysis**

172 The primary analysis will be based on the intention-to-treat principle, including everyone
173 who were randomized. Comparisons between arms will be conducted according to pre-
174 specifications in the protocol. These comparisons align well with the recommended
175 analysis and reporting of factorial trials⁵, which used “inside the table” and “at the
176 margin” analyses for different comparisons. The “inside the table” analysis will be used
177 to compare each intervention effect to control, while “at the margins” analysis will be
178 used to assess the effect of adding intervention.

179 The major interest would be the effect of the intervention on change in primary
180 outcomes at 6 Month compared to the control arm (arm 5). The primary outcome
181 measure of mean change in ADAS-Cog-13 and ADAS-Cog-Plus scores will be analyzed
182 using a linear mixed model with restricted likelihood estimation. The model will be fitted
183 with participant-specific random intercept and fixed effects of time, intervention arm, and
184 time x intervention arm interaction. The time variable will be used as a categorical
185 variable (0 = baseline; 1 = Month 6.) The intervention arm variable will be dummy

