186 coded, using the control group as a reference category. The interaction term will be

187 used to assess between-group differences (representing a mean difference in change in
188 cognitive scores over time between two groups). With dummy coding of the intervention
189 arm, the interaction term will allow to compare the mean change in each intervention
190 arm to the arm 5 (control). The within-group difference (representing a mean change in
191 cognitive scores over time within the group) will be measured with marginalized mean
192 from the linear mixed regression model. The model will be further adjusted for
193 participant characteristics including age, sex, education, and comorbidities.

194 An unstructured covariance matrix will be used for all models. The model assumption
195 will be assessed using the normal quantile plots of residuals for normality and the
196 residuals vs. fitted plot for variance homogeneity. If the assumptions are not fully met,
197 the data will be transformed (i.e., log). Missing data will not be imputed and will be
198 assumed to be missing at random, as the mixed model approach is well-known to
199 handle such data effectively.⁶ The baseline data from individuals who did not complete
200 Month 6 assessment will be included in the linear mixed model.

201 The mean difference between groups will be presented with their 95% CI and p-value,
202 while the mean change within group will be presented with their standard error. The
203 obtained marginalized mean and standard deviation will be used to calculate the effect
204 size (
$$\frac{\text{mean change in treatment } X - \text{mean change in treatment } Y}{\text{pooled standard deviation of change}}$$
). As outlined in our published
205 protocol, we will calculate the proportion of participants with improvement in primary
206 outcomes.

207 All tests will be two-sided, and p-value of less than 0.05 will be considered as
208 statistically significant. Adjustments for multiple comparisons will not be made as the
209 trial is intended to compare the intervention effect to the control rather than pairwise.⁷
210 Per-protocol analysis will be performed as well.

211 As per recommended analyses of fractional factorial design⁸, “at the margin” analyses
212 will be performed by collapsing arms according to the pre-specified comparison.
213 Collapsing intervention arms allow to increase the study power to detect the difference

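### Withdrawal for dementia or another listed event can end outcome collection before Month 6, and the missing-at-random assumption of the two-visit primary model may not hold for those participants

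*Combined protocol and SAP*

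**What the plan says.** Protocol section 9.3 opens: "Participants may be withdrawn or be discontinued from the study for any of the following reasons". Besides the participant's request, investigator discretion and intolerable or life-threatening adverse events, it lists renal dysfunction, dementia, severe depression, anxiety or schizophrenia, and hypercalcaemia and/or hypermagnesemia. It closes: "Participant data collected to the date of discontinuation or withdrawal will be included in the analysis". Section 9 adds that, after an adverse event, the team leader may decide to end a person's participation. Neither section says whether outcome visits continue once the intervention has stopped.

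The SAP puts the endpoint at Month 6 (section 5) and defines the primary outcome as change in ADAS-Cog-13 and ADAS-Cog-Plus, where a higher score is worse (section 8). Section 10.2 says: "The primary analysis will be based on the intention-to-treat principle, including everyone" randomised. The primary model is a linear mixed model with time coded as baseline or Month 6. On missing values the same section says "Missing data will not be imputed and will be" and continues "assumed to be missing at random, as the mixed model approach is well-known to" deal with them. "The baseline data from individuals who did not complete" Month 6 stays in the model. I found no sensitivity analysis for data missing not at random, no rule for handling dementia in the analysis, and no table of withdrawal reasons by arm. The per-protocol analysis does not fill that gap.

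**The concern.** Dementia is not an incidental reason for loss in a trial whose endpoint is cognition. It marks the people whose scores have worsened most. If someone is withdrawn for it before Month 6, the model sees only the baseline score, plus age, sex, education and comorbidities in the adjusted version. Those variables predict later decline only in part, and there is no intermediate score to carry the rest. Whether the Month 6 value is missing may then depend on that unseen value.

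At stake is the contrast between arms. If an intervention prevents conversion, control loses more decliners than the active arms and a true benefit is understated. Hypercalcaemia is a second possible source of uneven loss, since sections 9.1 and 9.2 tie it to vitamin D. The documents give no link from it to ADAS-Cog, so it is left out of the figures below.

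**Working it through.** **The plan's own figure.** The only stated number on missing data is the dropout allowance in protocol section 5.3: 34 / (1 − 0.15) = 40 per arm, × 5 = 200. This reproduces. It covers how many are lost, not why.

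**When loss can occur.** CDR is scheduled at screening, Month 6 and Month 12 (protocol 7.1, 7.3, 7.5; SAP Table 1). Calcium is drawn at baseline and again at Month 6 (7.6.3). ADAS-Cog is taken at the same Month 6 visit. An event first found at that visit can leave an ADAS-Cog score in the data. The primary endpoint is lost only when the event comes to light clinically before Month 6 and the option to withdraw is used.

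**Simple arithmetic.** Let pC and pA be the shares of control and active participants lost for dementia before Month 6, and d their excess worsening over those who remain, not predicted by baseline. Each arm's mean change then looks better by p × d, so

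hidden benefit = (pC − pA) × d.

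The documents give neither p nor d. Assumed: pC = 3–8%, pA = half of pC, d = 5–8 points, all converters lost.

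- Low: (0.03 − 0.015) × 5 = 0.075 points
- Middle: (0.05 − 0.025) × 5 = 0.125 points
- High: (0.08 − 0.04) × 8 = 0.32 points

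Against the protocol's 3-point effect: 0.075 / 3 = 2.5% and 0.32 / 3 = 10.7%. Against 1.5 points (SAP d of about 0.5 × protocol SD of 3): 5% and 21%. The 1.5 is approximate, because the SAP's d refers to changes while the protocol quotes its SD beside a mean score.

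In people, 3–8% of 40 controls is 1.2 to 3.2. If pC = pA with the same d, the bias is 0. If active loses more, the sign turns: with 4% of control and 10% of active lost and d = 3–9, benefit is overstated by 0.18–0.54 points.

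**Simulation of the mechanism.** Baseline and Month 6 scores are bivariate normal, SD 3 (protocol 5.3), with an assumed correlation of 0.7. Month 6 scores above a cut-off are removed. The cut-off takes out the worst 5%, 10% or 15% of controls and is the same in active. Estimation is by likelihood under missing at random.

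| True difference | 5% | 10% | 15% | Loss depends on baseline only |
|---|---|---|---|---|
| −3 | −2.83 | −2.70 | −2.57 | −3.0 |
| −1.5 | −1.38 | −1.29 | −1.21 | −1.5 |
| 0 | 0 | 0 | 0 | 0 |

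If only half of those above the cut-off are withdrawn, a true −1.5 is estimated as −1.45, −1.42 and −1.40. The estimate shrinks only when loss depends on the Month 6 value itself.

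**The case against.** The strongest reply is that the rule mostly misses the primary endpoint. Dementia rating, calcium and ADAS-Cog share the Month 6 visit, section 9.3 keeps data collected up to withdrawal, and withdrawal is permitted rather than required. The intervention lasts 20 weeks, so few people may convert, and the rates and decline used above are assumptions. All of this stands, and it is why the size at Month 6 is probably small. It does not remove the gap: earlier clinical detection is possible, sites may use the option differently, and no text protects the Month 6 assessment when they do.

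Four stronger readings are tempting, and the documents do not support them.

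- *The missing-at-random assumption fails.* It may fail. Loss is not automatic, and baseline and covariates carry some information.
- *Intention-to-treat is breached.* The SAP keeps baseline data from those without Month 6, so they remain in the analysis. What they lack is an outcome, which is a missing-data problem.
- *The bias is larger at Month 12.* SAP section 10.2.5 uses three time points, so someone withdrawn at or after Month 6 contributes that score and missing at random becomes more plausible. More conversions could work the other way. The direction is not established.
- *The rule manufactures a benefit.* With no true effect and the same rule in every arm, the simulated bias is zero.

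**Conclusion.** The point holds as a gap in the plan, not as a demonstrated bias. Section 9.3 allows outcome collection to end for a reason closely tied to the outcome, and the SAP relies on missing at random in a two-visit model without testing it. A true benefit would shrink if control loses more decliners, and would be overstated if active does. On the stated assumptions the hidden benefit is about 0.08–0.32 points, roughly 3–11% of a 3-point effect or 5–21% of a 1.5-point effect. Because these assume that every converter by Month 6 is lost, the shared Month 6 visit and the permissive rule would make the effect smaller for the same conversion rates. It is worth correcting because the correction is cheap and protects the primary endpoint. Confidence is medium.

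**What to change.** **Protocol 9.3.** Leave the clinical criteria and the timing of stopping as they are. Add that discontinuation for a listed event does not by itself end outcome follow-up. Offer the already scheduled Month 6 and Month 12 cognitive assessments unless consent to follow-up is withdrawn or assessment is not feasible, and include those scores in the intention-to-treat analysis.

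**SAP 10.2.** Tabulate withdrawals by reason and arm. Add a delta-adjusted or reference-based sensitivity analysis for missing Month 6 scores. If data collection can no longer be changed, these two steps can still be done.

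**Cost.** A few assessments in participants no longer on intervention, some of whom may be unable to complete them, and slightly more analysis. No new visits are needed.

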10. ETHICAL CONSIDERATIONS

This study will be conducted in compliance with the outlined protocol, International Conference on Harmonization Good Clinical Practice (ICH-GCP), and all applicable regulatory requirements.

All relevant documents for this study will be submitted to the appropriate Research Ethics Board (REB) for review. Written approval from the REB must be obtained prior to entering and testing participants within this study. The REB will be notified of any protocol amendments regarding new study procedures which may occur during the course of the study. Written approval from the REB on these amendments must be received prior to implementation of any new procedures.

10.1 CONFIDENTIALITY OF PARTICIPANT RECORDS

Participants will be identified by a study identification number. It will be necessary to collect the participants name and contact information as this study will require several scheduling procedures. This information will be kept separate from the participant study identification number.

11. ADMINISTRATIVE REQUIREMENTS

11.1 PROTOCOL AMENDMENTS

The leaders of the study, in collaboration with members of the team, may modify the protocol at any time during the study. Protocol amendments will require REB approval prior to implementation of any changes.

11.2 COMPLETION OF CASE REPORT FORMS (CRFS)

All sites participating in this study will be trained on completion of CRFs. The primary investigators at all sites are responsible for the CRFs with respect to completeness, accuracy, and clarity.

11.3 MONITORING PROCEDURES

All sites will use the same data collection forms to maintain consistency. Monitoring procedures will be performed using the LORIS system platform for uploading data specially developed for the SYNERGIC study by CCNA informatics team platform.

12. PUBLICATION POLICY

The SYNERGIC Trial will follow CCNA publication policy.

12.1 PARTICIPATING CENTERS

The following centers will be participating in this study:

- Gait and Brain Lab & Neurovascular Research Lab, The University of Western Ontario, London, ON
- Imaging Research Laboratories, Robarts Research Institute, The University of Western Ontario, London, ON
- Aging, Mobility, and Cognitive Neuroscience Lab, University of British Columbia, Vancouver, BC
- Brain Research Centre, Centre for Hip Health and Mobility

- Unité de Neuroimagerie Fonctionnelle, Centre de recherche, Institut universitaire de gériatrie de Montréal, Université de Montréal, Montreal
- Division of Geriatrics, McGill Centre of Excellence in Aging and Chronic Disease, McGill University
- PERFORM Center, Concordia University/Centre de recherche, Institut universitaire de gériatrie de Montréal, Université de Montréal (CRIUGM)
- Department of Psychology, Concordia University
- Department of Medicine, Division of Neurology, University of Alberta
- The Sun Life Financial Movement Disorders Research and Rehabilitation Centre, Wilfrid Laurier University
- Centre for Community, Clinical and Applied Research Excellence (CCCare), University of Waterloo
- Balance, Mobility and Falls Clinic at Toronto Rehab Rehabilitation Affiliate Network of the Centre for Stroke Recovery, Sunnybrook

Figure 1: CONSORT flowchart for the SYNERGIC Trial

[figure not shown]
[figure not shown]

Figure 2. Schematic Timeline of Synergic Trial

[figure not shown]
^(a) Recruitment of participants will be an on-going process with individuals being assigned to groups as they are enrolled. Recruitment period is expected to be 24 months, at a recruitment rate of 2.5 patients per month per main site (conservative estimate). However, recruitment may continue up to 36 months after the first individual has been recruited. Recruitment period of 24 months

^(b) Baseline assessments (T0) will be completed within one-week of participant starting the specific intervention/placebo (i.e. month 0 for the first participant recruited; and month 30 for the last participant recruited). Participants will return to the clinic six months^(c) after starting the specific intervention/placebo (T6) to complete the post intervention assessment.

Six months participants will return to the clinic again (T12) at which time their final assessment will be completed. The same assessments at T0 will be done.

APPENDIX I

Procedure	Visit 1 Screening	Visit 2 Baseline	Randomization	Visit Table		
				Visit 3 6M Visit	Telephone Follow-up (9M post-Baseline)	Visit 4 12M Visit
Written Informed Consent	X					
Demographic Information	X					
PASE Questionnaire	X			X		X
Mini Mental State Examination (MMSE)	X					
Montreal Cognitive Assessment (MoCA) Logical Memory 1 & 2 *	X			X		X
CERAD Word List Recall *						
Geriatric Depression Scale (GDS-30)	X			X		X
Generalized Anxiety Disorder 7 (GAD-7)	X			X		X
Clinical Dementia Rating (CDR)	X			X		X
Physical Activity Readiness Questionnaire Plus (PAR-Q +)	X					
ADCS-ADL and IADL	X			X		X
Clinical Medical Questionnaire		X		X		X
Dual Task Control Assessment		X		X		X
Six Minute Walk Test (6MWT) ^		X		X		X
Quality of Life Questionnaire (SF-36)		X		X		X
ADAS-Cog 13 (+ tests **)		X		X		X
Digit Span Forward and Backward WAIS-III **		X		X		X
TMT A and B **		X		X		X
Digit Symbol Test **		X		X		X
Boston Naming Test **		X		X		X
Colour Word Interference Test		X		X		X
Envelope Test		X		X		X
Short Physical Performance Battery (SPPB)		X		X		X
Gait Assessment using Gait Mat and accelerometers (when available)		X		X		X
Neuroimaging (MRI)		X		X		
Blood Draw		X		X		X
Falls Calendar ^^		X		X	X	X

* These tests are implemented to harmonize with inclusion criteria for COMPASS-ND and are not mandatory if the MoCA score ≤ 24 .

** Testing included in the ADAS Cog Plus.

^ 6MWT can be completed at the Baseline Visit or at Day 1 of intervention sessions at the gymfacilities. Please note date and location of the 6MWT in patient file.

^^ Calendar will be given to participant to complete and will be submitted to Research Staff at exercise training.

1
2
3
4
5
6
7

Statistical Analysis Plan (SAP)

10
11
12
13 **SYNchronizing Exercises, Remedies in Galt and Cognition (SYNERGIC) Trial**

13 SYNchronizing Exercises, Remedies in Galt and Cognition (SYNERGIC) Trial

14
15
16
17
18
19
20
21
22
23

Version: Final

Authors: [name], PhD, University of Western Ontario
[name](c), University of Western Ontario
[name], Parkwood Institute
[name], University of Western Ontario and Robarts Research Institute
[name], University of Western Ontario

Date: Sept 2022

24
25
26
27
28
29
30

31 1. Introduction

32 The SYNERGIC TRIAL (SYNchronizing Exercises, Remedies in Galt and Cognition) is
33 a randomized, phase II, fractional factorial, five-arm, double-blind controlled study
34 evaluating the effect of aerobic-resistance exercise with and without cognitive training
35 and vitamin D supplementation on cognitive function.

36 Specifically, physical exercise is a progressive and supervised aerobic (AE) and
37 resistance training (RT) program tailored for older adults' physical capabilities.
38 Computerized cognitive training will be delivered using the Neuropeak cognitive training
39 program designed to target working memory and attention. Vitamin D supplementation
40 will be delivered in capsules with 10,000 IU, 3 times per week, reaching a weekly dose
41 of 30000 IU. Control interventions will be sham cognitive training, balance and toning
42 exercise (BAT), and matching vitamin D placebo capsules.

43

44 2. Study Objectives

45 To evaluate:

46 **Objective 1** The effect of supervised aerobic-resistance exercise on cognitive function

47 **Hypothesis 1.** Twenty weeks of supervised aerobic-resistance exercise will significantly
48 improve cognitive function in older adults with MCI, as assessed by primary outcome
49 Alzheimer's Disease Assessment Scale-Cognitive (ADAS-Cog 13 and plus variant) and
50 secondary outcomes, compared to a balance and toning (BAT) control.

51 **Objective 2.** The effect of adding cognitive training to aerobic-resistance exercise on
52 cognitive function.

53 **Hypothesis 2.** Adding cognitive training to aerobic-resistance exercise will significantly
54 improve primary and secondary outcomes compared to aerobic-resistance exercise
55 without cognitive training.

56 **Objective 3.** The effect of adding vitamin D supplementation to aerobic-resistance
57 exercise on cognitive function.

58 **Hypothesis 3.** Adding vitamin D supplementation in weekly dose of 30000 IU to
59 aerobic-resistance exercise will significantly improve primary and secondary outcomes
60 compared to aerobic-resistance exercise without vitamin D supplementation.

61 **Objective 4.** The effect of multi-domain intervention (aerobic-resistance exercise +
62 cognitive training + Vitamin D supplementation) on cognitive function.

63 **Hypothesis 4.** The multi-domain intervention (aerobic-resistance exercise + cognitive
64 training + vitamin D supplementation) will significantly improve primary and secondary
65 outcomes compared to the control intervention.

66

67 3. Study Population

68 We will target older adults aged 60 to 85 years old with mild cognitive impairment (MCI).

69

70 4. Study Design

71 This is a Phase II, randomized, double-blind, five-arm controlled trial. The trial design
 72 follows a fractional factorial design as shown in Figure 1. Participants will be recruited
 73 primarily from the community and from clinics serving MCI population across five sites:
 74 London (lead and sponsor site), Waterloo-University of Waterloo, Waterloo-Wilfrid
 75 Laurier University, Montreal, and Vancouver. All eligible participants will be randomized
 76 to 5 arms in 1:1:1:1:1 ratio:

[figure not shown]
77 Arm 1: combined AE and RT exercise + cognitive training + vitamin D

78 Arm 2: combined AE and RT exercise + cognitive training + placebo vitamin D

79 Arm 3: combined AE and RT exercise + control cognitive training + vitamin D

80 Arm 4: combined AE and RT exercise + control cognitive training+ placebo vitamin D

81 Arm 5: BAT exercise + control cognitive training + placebo vitamin D

82 AE: aerobic exercise; RT: progressive resistance training; BAT: balance and toning control

83 Figure 1. Trial design overview

84 5. Study Endpoint

85 The study endpoint will be at 6 Month (post-intervention).

86

87

6. Study Assessment

88 The participant's eligibility will be assessed during the screening visit. Assessment
 89 which will be performed during three visits: baseline, post-intervention at 6 months, and
 90 6-month follow up after the postintervention at 12 months. The measures at each
 91 assessment are described in Table 1.

92

93 Table 1. Assessments across study visits

Procedure	Visit 1 Screening	Visit 2 Baseline	Visit 3 6 month	Telephone Follow-up at 9 month	Visit 4 12 month
Written Informed Consent	X				
Demographic Information	X				
Mini Mental State Examination (MMSE)	X				
Physical Activity Readiness Questionnaire Plus (PARQ +)	X				
Logical Memory 1 & 2	X				
CERAD Word List Recall	X				
PASE Questionnaire	X				
Montreal Cognitive Assessment (MoCA)	X		X		X
Generalized Anxiety Disorder 7 (GAD-7)	X		X		X
Geriatric Depression Scale (GDS-30)	X		X		X
Clinical Dementia Rating (CDR)	X		X		X
Activities of Daily Living (ADCS-ADL and IADL)	X		X		X
Clinical Medical Questionnaire		X	X		X
Dual Task Control Assessment		X	X		X
ADAS-Cog 13 (+ tests ^a)		X	X		X
Trail Making Test A & B ^a		X	X		X
Digit Symbol Test ^a		X	X		X
Digit Span Forward and Backward WAIS-III ^a		X	X		X
Boston Naming Test ^a		X	X		X
Verbal Fluency Test ^a		X	X		X
Colour Word Interference Test		X	X		X
Quality of Life Questionnaire (SF-36)		X	X		X
Short Physical Performance Battery (SPPB)		X	X		X
Gait Assessment using Gait Mats and accelerometers (when available)		X	X		X
Six Minute Walk Test (6MWT) ^b		X	X		X
Neuroimaging (MRI)					
Blood Draw		X	X		
Falls Calendar ^c		X	X	X	X

94 ^aTesting included in the ADAS-Cog plus95 ^bThis test may be completed at the gym facility on the first day of intervention96 ^cCalendar will be given to participant to complete and will be submitted to Research Staff at exercise training97

7. Determination of Sample Size

98 Sample size calculation is based on changes in our primary outcome: global cognitive
 99 function measured using the Alzheimer Disease Assessment Scale Cognitive 13 and

100 the plus variant (ADAS-Cog 13 and plus). A target sample of 200 participants (40 per
 101 arm) was determined based on 80% power to detect either main effects or an
 102 interaction of at least a moderate (Cohen's $d \sim 0.5$)¹ effect size of changes in the ADAS-
 103 Cog-13.² The final sample size accounted for a 15% attrition.

104

105 **8. Primary Outcomes**

106 Primary outcome will be changes in cognitive function measured with the ADAS-Cog 13
 107 items (ADAS-Cog-13) and the plus variant (ADAS-Cog-plus) at endpoint, 6 Month.
 108 Improvement at endpoint in either variant is considered evidence of efficacy.

109 **8.1 Change in cognitive function on ADAS-Cog-13 at post-intervention (Month 6)**

110 The ADAS-Cog 13 consists of 13 brief cognitive tests assessing memory, language,
 111 attention, concentration and praxis. The individual tests are listed in Table 2. Scores
 112 range from 0 to 84, with higher scores indicating severe cognitive impairment.

113 **8.2 Change in cognitive function on ADAS-Cog-Plus at post-intervention (Month 6)**

114 Four additional tests focusing on executive function will be added to the ADAS-Cog 13
 115 to comprise the plus variant³ (Table 2). Scores will be transformed into an algorithm
 116 validated by Crane et al.⁴ The higher scores will indicate severe of cognitive impairment.

117
 118 Table 2. Individual tests included in the ADAS-Cog

ADAS-Cog-13	ADAS-Cog-Plus
Word recall	Word recall
Delayed word recall	Delayed word recall
Following commands	Following commands
Constructional praxis	Constructional praxis
Ideational praxis	Ideational praxis
Naming objects	Naming objects
Orientations	Orientations
Word recognition	Word recognition
Remembering instructions	Remembering instructions
Comprehension	Comprehension
Word finding	Word finding
Spoken language	Spoken language
Number cancellation	Number cancellation
	Trial Making A and B
	Digit symbol substitution
	WAIS III digit forward and backward
	Category fluency – Animals and Vegetable

119 **9. Secondary Outcomes^{*}**

120 Secondary outcomes include neuropsychological assessments, gait and mobility
121 outcomes (including incidence of fall), neuroimaging, and blood biomarkers. *Note that
122 secondary outcomes will be not reported in the primary manuscript.

123 **9.1 Change in cognitive function on neuropsychological tests**

124 The secondary cognitive outcomes will include:

125 a) Montreal Cognitive Assessment test for global cognition
126 b) The ADAS-Cog Recall word list for verbal semantic memory
127 c) Trail Making Test A and B
128 d) Digit Symbol Substitution Test
129 e) Digit Span Test Forward and Backwards
130 f) Boston Naming Test
131 g) Verbal fluency Animals and Vegetables

132 **9.2 Change in gait performance**

133 Gait performance will be evaluated using gait speed and gait variability under single and
134 dual-tasking. Gait speed will be measured as the time taken to walk 6 m using an
135 electronic walkway system (ProtoKinetic® and/or GAITRite® Systems, Inc.). Gait
136 variability of spatial and temporal gait variables (stride time, stride length, double
137 support time and step width) will be calculated using the coefficient of variation (CV =
138 (standard deviation / mean) ×100).

139 **9.3 Change in mobility and falls**

140 Mobility will be measured with the Short Physical Performance Battery (SPPB), and the
141 6 min walk test (6MWT).

142 A fall will be defined as 'unintentionally coming to rest on the ground, floor, or other
143 lower level and not due to a seizure, syncope, or an acute stroke'. Recurrent falls are
144 defined as 'two or more events in a 12-month period'. Falls will be recorded throughout
145 the 12-month trial, participants will be provided with a falls calendars, on which they will
146 record any falls that have occurred, and they will be asked to bring them monthly to the
147 training sessions to review with a research staff member. After the completion of the
148 intervention, participants will be contacted at month 9 and 12 to report incidental falls.

149 **9.4 Change in Neuroimaging**

150 Pre-post regional patterns of brain plasticity will be assessed using structural (high-
151 resolution 3D T1-weighted images = 7 min) in order to get voxel-based volumetric and
152 cortical thickness measures, as well as diffusion tensor imaging (DTI, 30 directions, with

153 AP/PA correction scan = 7 min) to calculate fractional anisotropy and diffusivity in white
154 matter tracts as well as derive tract-based statistics. Cerebrovascular integrity and
155 pathology will be assessed using the following contrasts: PD/T2 = 5 min; FLAIR = 7 min,
156 and T2* = 5 min). Functional magnetic resonance imaging at rest (rsfMRI plus field map
157 = 12 min) will also be acquired to measure change in data-driven functional networks.

158 **9.5 Change in Blood biomarkers measures**

159 Serum biomarkers of inflammation (C reactive protein, and interleukin 6), neuroplasticity
160 (brain-derived neurotropic factor), endothelial health (vascular endothelial growth factor
161 1), and vitamin D serum levels will be measured before and after intervention.

162 **9.6 Covariates**

163 Pre-specified covariates will be age, sex, years of education and number of
164 comorbidities.

165

166 **10. Statistical Analysis**

167 **10.1 Descriptive Analysis**

168 The baseline characteristics will be summarized using means and standard deviation, or
169 medians and interquartile range where appropriate, for continuous characteristics, and
170 frequencies and percentages for categorical variable.

171 **10.2 Primary Efficacy Analysis**

172 The primary analysis will be based on the intention-to-treat principle, including everyone
173 who were randomized. Comparisons between arms will be conducted according to pre-
174 specifications in the protocol. These comparisons align well with the recommended
175 analysis and reporting of factorial trials⁵, which used “inside the table” and “at the
176 margin” analyses for different comparisons. The “inside the table” analysis will be used
177 to compare each intervention effect to control, while “at the margins” analysis will be
178 used to assess the effect of adding intervention.

179 The major interest would be the effect of the intervention on change in primary
180 outcomes at 6 Month compared to the control arm (arm 5). The primary outcome
181 measure of mean change in ADAS-Cog-13 and ADAS-Cog-Plus scores will be analyzed
182 using a linear mixed model with restricted likelihood estimation. The model will be fitted
183 with participant-specific random intercept and fixed effects of time, intervention arm, and
184 time x intervention arm interaction. The time variable will be used as a categorical
185 variable (0 = baseline; 1 = Month 6.) The intervention arm variable will be dummy
186 coded, using the control group as a reference category. The interaction term will be

187 used to assess between-group differences (representing a mean difference in change in
188 cognitive scores over time between two groups). With dummy coding of the intervention
189 arm, the interaction term will allow to compare the mean change in each intervention
190 arm to the arm 5 (control). The within-group difference (representing a mean change in
191 cognitive scores over time within the group) will be measured with marginalized mean
192 from the linear mixed regression model. The model will be further adjusted for
193 participant characteristics including age, sex, education, and comorbidities.

194 An unstructured covariance matrix will be used for all models. The model assumption
195 will be assessed using the normal quantile plots of residuals for normality and the
196 residuals vs. fitted plot for variance homogeneity. If the assumptions are not fully met,
197 the data will be transformed (i.e., log). Missing data will not be imputed and will be
198 assumed to be missing at random, as the mixed model approach is well-known to
199 handle such data effectively.⁶ The baseline data from individuals who did not complete
200 Month 6 assessment will be included in the linear mixed model.

201 The mean difference between groups will be presented with their 95% CI and p-value,
202 while the mean change within group will be presented with their standard error. The
203 obtained marginalized mean and standard deviation will be used to calculate the effect
204 size (
$$\frac{\text{mean change in treatment } X - \text{mean change in treatment } Y}{\text{pooled standard deviation of change}}$$
). As outlined in our published
205 protocol, we will calculate the proportion of participants with improvement in primary
206 outcomes.

207 All tests will be two-sided, and p-value of less than 0.05 will be considered as
208 statistically significant. Adjustments for multiple comparisons will not be made as the
209 trial is intended to compare the intervention effect to the control rather than pairwise.⁷
210 Per-protocol analysis will be performed as well.

211 As per recommended analyses of fractional factorial design⁸, “at the margin” analyses
212 will be performed by collapsing arms according to the pre-specified comparison.
213 Collapsing intervention arms allow to increase the study power to detect the difference
